#### **15.3.4 Laboratory Parameters**

Descriptive statistics will be presented for observed and change from baseline values of each laboratory parameter (BUN, Cr, Na+, K+, Cl, C02, and Mg) and cardiac biomarker (NT-proBNP). Individual subject data listings of laboratory results will be presented. The clinically significant (defined as greater than twice the upper reference value or less than  $\frac{1}{2}$  the lower reference value) laboratory results will also be flagged.

Additionally, Laboratory data will be summarized by displaying shifts from baseline result (Low/Normal/High) to post-baseline visits by treatment group.

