3.2.3. Adverse Events of Special Interest over 30 Days

- Worsening kidney function, defined as increase of ≥ 0.5 mg/dl in serum creatinine
- Hyperkalemia, defined as $K > 5.5$ mEq/L
- Hypokalemia, defined as $K < 3.5$ mEq/L
- Hypomagnesemia, defined as $Mg < 1.5$ mg/dL

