6.2.13. Clinical Laboratory Tests

All routine samples will be analyzed by a local licensed clinical laboratory. The clinical laboratory tests are as follows:

- **Blood Clinical Chemistry:** blood urea nitrogen (BUN), creatinine, sodium, potassium, chloride, bicarbonate, magnesium
- **Urine pregnancy test:** β hCG test.

The Investigator is responsible for determining if out-of-range laboratory values are clinically significant or not. All clinically significant values will be followed until stabilization, resolution, or loss to follow-up or until no further improvement is expected.

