### 10.3 Adverse Events of Special Interest over 30 Days

- Worsening kidney function, defined as increase of  $\geq 0.5$  mg/dL in serum creatinine
- Hyperkalemia, defined as  $K > 5.5$  mEq/L
- Hypokalemia, defined as  $K < 3.5$  mEq/L
- Hypomagnesemia, defined as  $Mg < 1.5$  mg/dL

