## 15. STATISTICAL ANALYSIS

This is a multicenter, randomized, open label, controlled study evaluating the effectiveness and safety of the Furoscix Infusor versus continued medical therapy in patients with chronic heart failure and fluid overload requiring augmentation in diuretic therapy outside of the acute care setting. The SAP takes precedence over the protocol.

Unless otherwise specified, all baseline data, including demographic data and other clinical characteristics will be compared using descriptive statistics grouped by treatment group (Furoscix On-Body Infusor vs Continued Medical Therapy for Worsening Heart Failure). Change from baseline is the absolute change, unless stated otherwise; which then will be percentage change from baseline. Tables will include footnotes indicating definition implemented. Continuous data will be summarized by reporting the number of observations, mean, standard deviation, minimum, median, and maximum values. Categorical data will be described using frequency tables showing the number and percentage of subjects falling within a particular category. Shift tables will be given where appropriate to show change at follow-up compared to baseline values.

Between-group analyses of baseline characteristics will employ descriptive statistics. Mortality and morbidity events will be assessed using appropriate statistical tests. The primary endpoint will be compared between treatments using the Finkelstein-Schoenfeld Method, comparing components of the composite endpoint between patients hierarchically. Given the nature of the study, there will be no imputation of missing data on endpoints.

The primary endpoints including CV death at 30 days, HF hospitalization at 30 days, Urgent ED/Clinic visit at 30 days for WHF (defined as IV diuretics, augmentation of or new administration of metolazone), and change in NT-proBNP from baseline at 7 days will also be summarized and analyzed separately.

In general, secondary efficacy with follow-up timepoints will be analyzed using Generalized Estimating Equations (GEE) models.

Statistical tests will be performed at a two-sided alpha level of 0.05, unless otherwise specified. Given the nature of the study, there will be no adjustment for multiple comparisons.

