  - If tied, score=0 for Patient B.

A listing of each endpoint for the composite will be presented for the ITT population.

A sensitivity analysis will be conducted where the primary efficacy endpoint analysis will be conducted on the ITT and PP analysis population and will exclude patients with normal NT pro-BNP values (defined as <125 pg/mL) at baseline. Results will be descriptively compared to the primary efficacy endpoint analysis on the ITT and PP population.

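### The SAP's 'clinically significant' laboratory flag is set too far out to mark the potassium and magnesium values, or track the creatinine rise, that the trial itself defines as events of special interest

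*SAP*

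**What the plan says.** SAP 15.3.4 plans descriptive statistics for "each laboratory parameter (BUN, Cr, Na+, K+, Cl, C02, and Mg) and cardiac biomarker (NT-proBNP"), then individual listings, and then says that clinically significant results will also be flagged. Significance is "defined as greater than twice the upper reference value or less than" half the lower reference value. The section adds shift tables from baseline in Low/Normal/High categories. It specifies no table or test of flagged results.

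The AESI limits are in Protocol 3.2.3 and SAP 10.3: "Hyperkalemia, defined as $K > 5.5$ mEq/L", "Hypokalemia, defined as $K < 3.5$ mEq/L", magnesium below 1.5 mg/dL, and "Worsening kidney function, defined as increase of" at least 0.5 mg/dL in serum creatinine.

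Three other provisions bear on the flag:

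- Protocol 6.2.13 uses the same term differently: "The Investigator is responsible for determining if out-of-range laboratory values are clinically significant or not".
- SAP 15 states: "The SAP takes precedence over the protocol".
- A sensitivity analysis in SAP 15.2.1 will "exclude patients with normal NT pro-BNP values (defined as <125 pg/mL) at baseline". This is the only normal limit for NT-proBNP that the documents give.

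**The concern.** Potassium, magnesium and sodium move within a narrow band. Doubling the upper limit or halving the lower one puts the flag far outside that band, so a potassium or magnesium value that the trial counts as an AESI goes unmarked. The creatinine AESI is a change from baseline, whereas the flag looks only at the level.

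Renal function and electrolytes are a secondary endpoint, AESI incidence is a primary endpoint, and the primary objective is pilot data on effectiveness and safety for a pivotal trial. In some places the listing flag may be the only marker a reader sees:

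- SAP 7.1 puts unscheduled and repeat assessments in listings and keeps them out of tables and figures. Protocol 6.2.10 allows safety laboratory tests at unscheduled visits, which are for subjects who are getting worse.
- SAP 15.3.3 tabulates AESIs by MedDRA class and term, which suggests recorded adverse events. Protocol 7.1 generally does not count a laboratory abnormality as an adverse event without symptoms or intervention. A symptomless low potassium may therefore not reach the AESI table.

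**Working it through.** The plan gives no derived figure to reproduce. The check applies the rule to the documents' own limits.

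**Rule.** Flag if the value is above 2 × upper limit (ULN) or below 0.5 × lower limit (LLN).

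**Inputs from the documents.** AESI limits: K 5.5 and 3.5 mEq/L, Mg 1.5 mg/dL, creatinine rise 0.5 mg/dL. Entry potassium: 3.6 to 5.4 (Protocol 4.2). NT-proBNP: normal below 125 pg/mL (SAP 15.2.1); entry sign at least 1000, or 1400 in atrial fibrillation (Protocol 4.1).

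**Assumed inputs.** Routine samples go to local laboratories and no reference ranges are given. Assumed: K 3.3–3.7 to 5.0–5.5 mEq/L; Mg LLN 1.5–1.8 and ULN 2.2–2.6 mg/dL; Na 133–137 to 143–148 mEq/L; creatinine ULN 1.0–1.35 mg/dL.

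**Flag limits**

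| Analyte | AESI limit | Flag, AESI limit as stand-in | Flag, assumed ranges |
|---|---|---|---|
| K high | >5.5 | 2 × 5.5 = >11.0 | >10.0 to 11.0 |
| K low | <3.5 | 0.5 × 3.5 = <1.75 | <1.65 to 1.85 |
| Mg low | <1.5 | 0.5 × 1.5 = <0.75 | <0.75 to 0.90 |
| Na high | none | – | >286 to 296 |
| Na low | none | – | <66.5 to 68.5 |

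With the entry limits as stand-ins, potassium gives 2 × 5.4 = 10.8 and 0.5 × 3.6 = 1.8.

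**Inverse check.** What reference limit would make the flag fire at the AESI limit?

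- K 5.5 needs ULN ≤ 5.5/2 = 2.75, below the trial's hypokalemia limit.
- K 3.5 needs LLN ≥ 2 × 3.5 = 7.0, above its hyperkalemia limit.
- Mg 1.5 needs LLN ≥ 2 × 1.5 = 3.0, above every assumed upper limit.

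For potassium, then, no coherent reference range rescues the rule, whatever the laboratory.

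**Creatinine.** The flag limit is 2 × (1.0 to 1.35) = 2.0 to 2.7 mg/dL. A rise of exactly 0.5 crosses it only from a baseline above 1.5 to 2.2. A subject already above the limit on Day 0 is flagged with no change at all.

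**NT-proBNP, if the flag covers it.** With ULN 125 the flag is 2 × 125 = 250. The entry sign is 1000/250 = 4 times that, and in atrial fibrillation 1400/250 = 5.6 times. Any ULN below 500 flags every value of 1000 or more.

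The sign is one of six, of which any two suffice. Qualifying combinations number 2^6 − 6 − 1 = 57, and those without the natriuretic peptide sign number 2^5 − 5 − 1 = 26. If a share q enters on NT-proBNP and a share r of the rest exceeds 250, the flagged share is q + (1 − q)r. For illustration only: 0.50 (q 0.5, r 0), 0.85 (q 0.7, r 0.5), 0.98 (q 0.9, r 0.8). The documents give neither q nor r.

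**The case against.** The strongest reply is that nothing planned depends on the flag. It sits beside the listings, with no count or test. Electrolyte and renal changes are shown independently in descriptive statistics and shift tables (SAP 15.3.4), AESI tables (15.3.3) and a GEE model of creatinine change (15.2.2). Protocol 6.1.3 also directs monitoring for these AESIs from blood drawn at each clinic visit. AESI limits are not reference limits, and extreme values would still be flagged.

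Most of this stands, and it limits the point to the flag. It does not remove it. The shift tables and descriptive statistics omit unscheduled results, and the SAP does not say whether the AESI tables draw on laboratory values or on reported events.

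A reader might infer four stronger things that the documents do not support:

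- *The trial's safety message would be falsely reassuring.* The other displays do not use the flag.
- *NT-proBNP would be flagged in almost every entrant.* The sign is optional, BNP can replace it in patients not on Entresto, and SAP 15.2.1 provides for baselines below 125. The section also names NT-proBNP as a cardiac biomarker apart from the laboratory parameters, so coverage is unclear.
- *About 0 of 51 subjects would have an electrolyte flag.* The documents give no distribution from which to predict a count.
- *The SAP overrides the investigator's judgement.* Protocol 6.2.13 and 7.7.3 govern follow-up and event recording at the site. A flag applied at analysis changes neither, despite the precedence sentence. What remains is one term with two meanings.

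**Conclusion.** The point holds as a minor defect in a listing flag. The rule leaves unmarked every potassium and magnesium value between the AESI limit and a far more extreme one: 5.5 to 11.0 and 1.75 to 3.5 mEq/L for potassium, and 0.75 to 1.5 mg/dL for magnesium, on the stand-in limits. The potassium result needs no outside range, since the inverse check covers all coherent ones. Magnesium and sodium rest on assumed ranges, but the answer is the same across them. Creatinine is misaligned because the AESI is a change and the flag is a level.

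For NT-proBNP only a conditional statement is justified. If the flag applies, with an upper limit of 125 (the central laboratory's limit is not given), and if the central baseline sample agrees broadly with the local eligibility result, every subject who qualified on NT-proBNP of 1000 or more is flagged at baseline. The share of all entrants is unknown.

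**What to change.** In SAP 15.3.4:

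- Delete the twice/one-half rule for the chemistry results.
- Flag potassium, magnesium and creatinine change from Day 0 at the cut-offs already in SAP 10.3. Use laboratory values, including those from unscheduled visits.
- Show the number of flagged subjects by arm. State this as an exception to SAP 7.1, which otherwise keeps unscheduled data out of tables.
- For BUN, sodium, chloride and CO2, mark Low or High against the local reference range.
- Reserve the term clinically significant for the investigator's judgement under Protocol 6.2.13, where that judgement is captured for the result.
- State that the flag does not apply to NT-proBNP.

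The cost is SAP wording, a programming change and one small table, and more results will be flagged. The numeric flags need no new data. The documents do not show whether the investigator's judgement is recorded for each laboratory result, so that element applies only where it is.

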### **15.3.5 Physical Examination**

The number and percentage of subjects within each body system will be presented.

Additionally, Physical Examination data will be summarized by displaying shifts from baseline result (Normal/Abnormal NCS/Abnormal CS) to post-baseline visits by treatment group.

### **15.3.6 Protocol Deviations**

Protocol deviations will be listed by treatment group including date, time point, deviation category, COVID related assessment and a description and explanation for the deviation.

### **15.3.7 COVID-19 Adverse Events**

If two or more COVID-19 positive cases are reported during the study, safety analyses will be conducted to compare rates between treatment arms and a comparison of rates to an external similar population diagnosed with COVID-19 if warranted.

### **15.3.8 Prior and Concomitant Medications (Non-CV, Non-Diuretic CV, Diuretic)**

#### Prior Medications

Prior medications will include any medication taken prior to subject's first dose of study medication i.e., Prior medications have a stop date/time before study treatment starts. Medications stopped on the same day as the start of first study-drug administration will be considered as prior medication only.

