5.7. Prior and Concomitant Therapy

Prior and concomitant therapy will include all prescription medications and therapies. All information on prior (within the past 48 hours) and concomitant therapies will be recorded in the Subject's source and on the Subject's CRF. They should include the name of the therapy or drug and duration of the treatment (start and stop dates).

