6.2. Study Phases and Procedures

A Time and Events Schedule is provided in [Appendix 1](#).

The Screening Phase will be conducted in the clinic. All Subjects who sign the informed consent form and satisfy the inclusion/exclusion criteria will be enrolled into the trial on the same day as screening. NT-proBNP will be sent to centralized laboratory. Drug administration will start on the day of screening and enrollment after randomization.

The Treatment Phase will begin upon completion of screening through Day 29. Furoscix will be administered via the Furoscix Infusor whereby 80 mg is administered subcutaneously over 5 hours in a biphasic regimen (30 mg in the first hour, followed 12.5 mg/hour for the subsequent 4 hours). Within a single 24-hour period, the 80 mg dose can be repeated at the discretion of the investigator ≥ 2 hours after the completion of the first dose. Subjects should be transitioned back to their oral maintenance diuretic regimen when clinically indicated at the discretion of the investigator. After Subjects have been transitioned to their oral maintenance diuretic regimen, additional doses of Furoscix can be prescribed during the 30-day study period as needed based on the presence of congestion symptoms (dyspnea, edema, and/or excess weight gain) as determined by the investigator. No more than 7 doses of Furoscix is permitted during the 30-day study period. Additional doses beyond 7 requires approval by the medical monitor.

Prior to leaving the clinic on Day 0, the Subject and/or caregiver will be trained by the study staff on how to prepare the study product and apply it to their abdomen and remove it once the infusion is completed. The initial dose of the study product may be administered in the clinic or at home on the day of enrollment. Additional doses will be provided to the Subject for self-administration or administration by a caregiver in the home setting as directed by the investigator or study staff.

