### **8.2 For Partial End Dates:**

1. If the year is unknown, then do not impute the date but assign a missing value.
2. If the month is unknown, then assign “December.”
3. If the day is unknown, then assign the last day of the month.

After implementing the rules above, to determine whether AEs (or medications) with missing start or stop dates are pre-treatment or on/after treatment, the following strategy will be used:

1. If both start date and stop date are missing, then the most conservative approach is taken, and the AE (or medication) is considered to be treatment emergent (or concomitant medication).
2. If the start date is missing but the stop date is not missing and is on or after the day of study dose administration, then the most conservative approach is taken, and the AE (or medication) is considered to be treatment emergent (or concomitant medication).

3. If the start date is missing but the stop date is not missing and is before the day of study dose and after the date of signed informed consent, then the AE (or medication) is considered to be before treatment (or prior medication).
4. If the start date is not missing but the stop date is missing, then the most conservative approach is taken, and medication is considered to be concomitant while the AE is defined by start date.

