#### Concomitant Medications

Concomitant medications are defined as prescribed medications and therapies, and over the counter (OTC) preparations, including herbal preparations and vitamins, other than Study medication taken during the study i.e., Concomitant medications are medications taken by subject on/after the start of first study-drug administration. If a medication starts before study entry and continues through the study that will be considered both as prior and concomitant.

Prior and concomitant medication will be categorized by preferred Term and ATC level X class per World Health Organization Drug Dictionary (WHODRUG; Version Global C3 2021SEP) and will be summarized by treatment group and overall, for the Safety Population. The count and percentage of patients using each medication will be displayed. Patients who taken the same medication (in terms of PT) more than once will be counted only once for that medication.

All Prior and concomitant medications will be presented in a listing for the Safety Population.

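### SAP 15.3.8 classes a drug taken after device start on Day 0 and stopped that day as pre-treatment only, against the SAP's own definition of concomitant medication (minor)

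*SAP*

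**What the plan says.** SAP 15.3.8 gives two statements on prior medications. The first ends with a clause on timing: "Prior medications have a stop date/time before study treatment starts". The second deals with the dosing day: "Medications stopped on the same day as the start of first study-drug administration will be considered as prior medication only".

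On concomitant medications the same section says: "Concomitant medications are medications taken by subject on/after the start of first study-drug administration". It adds a rule for drugs that span both periods: "If a medication starts before study entry and continues through the study that will be considered both as prior and concomitant".

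SAP 8.2, rule 2, covers records without a start date. The condition reads "If the start date is missing but the stop date is not missing and is on or after the day of study dose administration", and the result is that the drug counts as concomitant, which the SAP calls the most conservative approach.

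On timing, Protocol 6.2 says: "Drug administration will start on the day of screening and enrollment after randomization". First dosing is therefore on Day 0. For drug records, Protocol 5.7 asks for the name and the "duration of the treatment (start and stop dates"). The Subject Diary (Protocol 6.2.24) also records date and time for oral diuretics taken on top of study drug.

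**The concern.** The same-day sentence has no condition on when the drug was started and none on clock time. Because it says the drug is prior and nothing else, a drug first given after device start and finished on Day 0 leaves the concomitant table and is shown as if it preceded treatment. Examples are a single added diuretic dose or a one-off treatment for a complaint during the infusion.

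The SAP thus gives two answers for one record, and two programmers could build different tables from it. The output at stake is the summary of prior and concomitant drugs, which the section heading splits into non-CV, non-diuretic CV and diuretic. In a diuretic trial that table is read for co-treatment. The pilot is also meant to refine analytical methods for a pivotal trial, so an uncorrected rule could be carried forward.

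**Working it through.** No figure in the plan needs reproducing; the check is to apply the rules to example records. The inputs are the same-day sentence, the stop-time clause and the concomitant definition (all SAP 15.3.8), rule 2 of SAP 8.2, and Day 0 as the day of first dosing (Protocol 6.2). For illustration, device start is assumed to be 12:00 on Day 0; only the order of events matters. Silent means that the sentence does not apply because the stop date is not Day 0.

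| Record | Same-day sentence | Stop-time clause | Meets concomitant definition |
|---|---|---|---|
| A. Stopped the day before Day 0 | silent | prior | no |
| B. Started earlier, last taken Day 0 08:00 | prior only | prior | no |
| C. Started earlier, last taken Day 0 18:00 | prior only | not prior | yes |
| D. Single dose Day 0 08:00 | prior only | prior | no |
| E. Single dose Day 0 18:00 | prior only | not prior | yes |
| F. Started Day 0 18:00, stopped Day 2 | silent | not prior | yes |
| G. Ongoing from before the study | silent | not prior | yes |
| H. Single dose Day 1 | silent | not prior | yes |
| I. Start missing, stopped Day 0 18:00 | prior only | not prior | yes; also under 8.2 rule 2 |

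Five records stop on Day 0 (B, C, D, E, I). For B and D the rules agree. For C, E and I the same-day sentence contradicts both the stop-time clause and the concomitant definition. The problem is therefore confined to drugs that have a Day 0 stop date and were taken after device start.

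The rule for drugs that are both prior and concomitant does not rescue E: it needs a start before study entry and continued use through the study.

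E and I can be the same drug, with the start date known in one record and missing in the other. If the same-day sentence is used for complete dates and rule 2 for missing ones, E is prior only and I is concomitant. The better-documented record gets the less cautious class.

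G shows a second, smaller conflict. A continuing drug has not stopped before treatment, so the stop-time clause excludes it from prior medication, while the spanning rule makes it both.

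Size: SAP 15.3.8 counts a patient once per Preferred Term. Let k be the number of Furoscix subjects whose only use of a term after device start carries a Day 0 stop date. If all 34 planned subjects are dosed and form the denominator, that row of the concomitant table is too low by k/34, or 1/34 = 2.9 percentage points per subject. The documents give no value for k; in principle it lies between 0 and 34.

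**The case against.** The strongest defence is that the sentence sits under prior medications, directly after drugs taken before the first dose are described, and so is meant as a tie-break for drugs already in use that end on Day 0. That is a fair guess at intent, but the text sets no such condition. The reading also fails for record C, a drug started earlier and last taken after device start, which is concomitant by definition and prior only by the tie-break.

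Second, clock times may settle the order. This stands in part. The diary gives times for added oral diuretics, and Protocol 5.7 names dates without excluding times; the CRF is not among the documents. But the same-day sentence works on days, so available times do not change its result.

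The objections to a larger claim stand in full. A reader might infer that every one-day Day 0 drug would show zero concomitant use. It would not: a subject who takes the same Preferred Term again later, or whose background drug continues under that term, is still counted. Nor are the drugs lost, since they stay in the prior table and the listing.

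A reader might also infer that the treatment effect or the safety picture would look cleaner than it was. The documents do not support that. The Finkelstein-Schoenfeld and GEE analyses do not draw on this classification. Adverse events are tabulated from adverse event records (SAP 15.3.1 to 15.3.3), with treatment emergence judged by onset or worsening (SAP 9).

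Nor can the table be called the only by-arm view of added diuretics. Urgent visits defined by IV diuretics or by new or augmented metolazone are compared by arm in SAP 15.2.1 and 15.2.1.1, and the mock tables mentioned in SAP 7.1 are not available here.

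**Conclusion.** The same-day sentence is wrong as written: it gives a classification that the rest of SAP 15.3.8 contradicts and, for missing start dates, that rule 2 of SAP 8.2 contradicts. Severity is minor. The consequence is limited to two descriptive tables in a 51-subject exploratory study, and to subjects whose only use of a term after device start ended on Day 0. How many there will be is unknown.

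This rests on a literal reading of the sentence. It also assumes that no unseen programming specification already overrides it.

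A related gap is that the rules are tied to first study-drug administration, which control subjects do not have, so the SAP gives no point from which to classify their drugs. Whether controls enter this table at all is a separate question, because SAP 14 defines the Safety population by at least one dose of Investigational Product.

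**What to change.** Replace the same-day sentence in SAP 15.3.8 with three rules:

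- A medication is prior only if it stopped before the reference time.
- A medication started at or after the reference time is concomitant, whatever its stop date.
- A medication that stopped on Day 0, and cannot be shown from available times (including diary times for oral diuretics) to have stopped before the reference time, is concomitant. It is also prior if it started before the reference time or if the order of its start is unknown.

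Use device start as the reference time for Furoscix subjects; SAP 15.2 already uses it as the reference for device use. State a reference time for control subjects, for example randomization.

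Reword the stop-time clause so that it agrees with the rule that a continuing drug is both prior and concomitant. Rule 2 of SAP 8.2 already fits as the date-based default, and rules 3 and 4 need no change for medications.

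Under these rules, and with the times as in the table, record E becomes concomitant, and C and I become both. B and D stay prior only where the stop time is known, and otherwise count in both tables.

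The cost is a few SAP sentences and one derivation line. No new CRF time field is needed, because the default covers unknown order. The small downside is that some drugs truly stopped just before dosing will count as concomitant, some of them in both tables.
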